Treatment period: At the Randomization Visit, eligible women will be randomized to 4 weeks of suvorexant or placebo. Pre-treatment symptom measures will be assessed at the Randomization Visit and interim and final on-treatment symptom measures will be assessed at the Interim Treatment Visit and Final Treatment Visit, respectively. The primary endpoint measures will be obtained at the Final Treatment Visit, conducted after 4 weeks on treatment. Participants will complete sleep and hot flash diaries for the 4 weeks they are on treatment and will be sent an Actiwatch and Biolog monitor to wear for one week (Actiwatch) and for one 24-hr period (Biolog) before returning them at the Final Treatment Visit. Participants will also be asked to provide saliva samples for two consecutive days in between Visits 1 and 2 and Visits 3 and 4. These samples will be used to measure cortisol. We have implemented these procedures in prior clinical trials

with efficiency and high levels of adherence. Adverse events will be assessed at each study visit using spontaneous-reporting adverse event procedures employed in our other clinical trials.

Intervention design: Suvorexant and identical placebo will be obtained from Merck and stored in the Brigham and Women’s Hospital Research Pharmacy. The Research Pharmacist will generate a confidential randomization schema using a block size of 4 to balance the one-to-one treatment assignment between the two study arms. Study participants and all study personnel, including those entering data, will be blinded to the assignment. Only the Research Pharmacist will be unblinded to treatment assignment.

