At the Randomization Visit, a one-week supply of suvorexant 10-mg pills or identical placebo will be given to each participant. Participants will be instructed to start taking 10-mg nightly for the first 7 days. At the Interim Treatment Visit conducted after one-week on treatment, participants who do not have treatment-limiting side effects will be instructed to increase the dose to 20-mg nightly. After the Interim Treatment Visit, women unable to tolerate a 20-mg dose will be given the option to reduce to a 10-mg dose. Consistent with FDA-approved directions, suvorexant will be started at 10-mg to first establish tolerability and then expected treatment efficacy will be optimized by increasing to the target 20-mg dose 7 days later. Any unused medication will be returned at the Final Treatment Visit, and unused pills will be counted as an indicator of adherence. If participants are unable to attend the Final Treatment Visit in person, subjects will complete remaining study procedures remotely, and will mail back any unused medication for a measure of adherence. Participants will also return the Actiwatch, Biolog monitor, and saliva samples by mail if a remote Final Treatment Visit is performed. In addition to answering questionnaires remotely, a study clinician will call the participant for safety monitoring. Study staff will review responses to the PHQ9 before ending study visits, and a study clinician will query participants directly about suicidal ideation and other adverse events at study visits while participants are on medication. Participants will not be informed of their treatment assignment at the Final Treatment Visit to maintain the blinding for study personnel.

Protocol Schema

[figure not shown]

Table of Procedures

		Screening		Intervention		
		Pre-V1	V1	V2 Random-ization	V3	V4
Study Week		-1	0	1	2	5
Weeks on Medication				0	1	4
Visit Location		Phone + Mail	Office	Office	Office	Office
General/ Screening Assessment	Screening Consent	X				
	Written Informed Consent		X			
	Health and Personal History Questionnaire		X			
	Insomnia Diagnostic Assessment		X			
	Medical History		X			
	Concomitant Medications	X	X	X	X	X
	Screening Assays (hepatic, renal, HCG, tox)		X			
	Hormone Assays (FSH, estradiol, progesterone)		X			
	Berlin Questionnaire	X				
Neck circumference		X				
PHQ-2	X					
Vitals	Height/Weight/Heart rate/Blood Pressure		X	X	X	X
	Waist to Hip Ratio		X			
Medication Dispensing & Instructions				X	X	
AE Reporting			X	X	X	X

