Potential risk to study subjects is minimized by the frequent visits and tests required by the study design. Careful screening procedures, including medical history and evaluation, laboratory tests, and psychological interviews, will facilitate the identification of any medical problems and potential adverse events so that subjects can be treated appropriately. At each visit, spontaneously reported adverse events will be noted by research staff. Any serious or non-serious adverse event will be recorded in the participant's study binder at each examination. Serious and non-serious adverse events will be reported to the Partners Human Research Committee in accordance with Human Research Committee reporting guidelines, following the timeframes specified by the Partners Investigator's Guidelines. In case of a serious adverse event, study medication will be unblinded and discontinued, and appropriate diagnostic and therapeutic measures will be taken, as determined by the investigator. All adverse event reports will be reviewed by the study physician.

The risks of the study are mainly from drug side effects, phlebotomy, and psychosocial risks.

Common side effects of suvorexant:

The most common side effects that were reported in previous studies with suvorexant included:

- Headache (7 out of 100 people reported this side effect)
- Next-day drowsiness (7 out of 100 people reported this side effect)
- Dizziness (3 out of 100 people reported this side effect)
- Abnormal dreams (2 out of 100 people reported this side effect)
- Cough (2 out of 100 people reported this side effect)
- Diarrhea (2 out of 100 people reported this side effect)
- Dry mouth (2 out of 100 people reported this side effect)
- Upper respiratory tract infection (2 out of 100 people reported this side effect)

Suvorexant may cause serious side effects that participants may not know are happening. These side effects include:

- Sleepiness during the day
- Not thinking clearly
- Acting strangely, confused or upset
- "Sleep-walking" or doing other activities when you are asleep like eating, talking, having sex, or driving a car.

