A Medical Monitoring Checklist has been developed to be included with each participant's binder, which triggers the Medical Monitor to double-check lab results, vital signs, concomitant medications, adverse events, and the scores on the Patient Health Questionnaire-9 (PHQ-9) at all visits.

Additional measures for assessing suicidal ideation

Several measures are in place to assess for suicidal ideation in participants throughout the study.

1. The Informed Consent form includes a statement informing participants to let study staff know if at any time they experience thoughts of self-harm or suicidal ideation during the study. The consenting clinician verbally confirms this statement prior to the participant signing the form.
2. Participants are screened by a study clinician for current Major Depressive Disorder and/or suicidal ideation at the Screening Visit after consent. Both are exclusion criteria for continued participation in the study. If excluded for depression or suicidal ideation, participants would be assessed by a study clinician for need for urgent care and referred to mental health services for treatment.
3. Participants complete the PHQ-9 at study visits while on medication. The PHQ-9 is completed on an iPad during the study visit. If a participant indicates thoughts of self-harm or suicidal ideation on the PHQ9, an alert is set to immediately send an email to the Principal Investigator, the Medical Monitor, the Sr. Project Manager, and the Research Coordinator.

4. Study staff review the responses to the PHQ9 before ending the study visit.
5. A study clinician will query participants directly about suicidal ideation and will inquire about adverse events at study visits while participants is on medication.
6. Any participant indicating emergence of suicidal ideation as determined by a study clinician will be taken off-study and referred to mental health services for further treatment.

Independent Safety Monitor

[REDACTED], will serve as the Independent Safety Monitor (ISM) for the remainder of this trial. The plan for Independent Safety Monitoring is as follows:

- In the case of a Serious Adverse Event (SAE), the study team will notify the ISM within 24 hours of becoming aware of the SAE. The ISM will review the case and, if appropriate, will examine the participant. The ISM will produce a short report on the SAE.

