- Every month, the ISM will review all Adverse Events. This review and any recommended actions will be documented in the Regulatory Binder.
- Upon completion of data collection, the final database will not be unblinded until the ISM has completed all reviews, protocol violators have been identified, and all study data are complete.

Adverse Event Reporting

Subjects will be closely monitored for adverse events at every visit. Research staff will record adverse events using standard spontaneous IRB-approved reporting procedures. Participants will be told during the consent process that they should report any changes in mood or thoughts of self harm immediately to the study team, using the contact information provided on the form. Participants will be informed that they can contact the investigator between visits if they have concerns about potential side effects. Routine adverse events and serious adverse events will be reported consistent with local IRB requirements and per Merck guidelines for reporting to the sponsor. In addition, the Medical Monitor and Independent Safety Monitor will review all adverse events and investigate those considered serious and unexpected consistent with standard ISM procedures.

X. REFERENCES

1. Ohayon MM. Severe hot flashes are associated with chronic insomnia. *Arch Intern Med*. 2006;166(12):1262-1268.

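### The clinician's adverse-event query has no stated content beyond suicidal ideation, so suvorexant effects that a participant may not notice may be under-recorded

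*Combined protocol and SAP*

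**What the plan says.** Three places describe adverse-event capture as spontaneous report. Section V, Treatment period: "Adverse events will be assessed at each study visit using spontaneous-reporting adverse event procedures employed in our other clinical trials". Section VII, Potential risks of study procedures: "At each visit, spontaneously reported adverse events will be noted by research staff". Section IX, Adverse Event Reporting: "Research staff will record adverse events using standard spontaneous IRB-approved reporting procedures".

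Two places describe something more active. Section V, Intervention design, says that "a study clinician will query participants directly about suicidal ideation and other adverse events at study visits while participants are on medication". Section IX, item 5 of the additional measures for suicidal ideation, says that a clinician queries suicidal ideation directly and "will inquire about adverse events at study visits while participants is on medication". If the final visit is remote, Section V adds a clinician telephone call for safety.

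On the effects themselves, Section VII (Common side effects of suvorexant) states: "Suvorexant may cause serious side effects that participants may not know are happening". Its list covers daytime sleepiness, clouded thinking, odd or confused behaviour, and walking, driving or other acts during sleep. Section V, Drugs to be used, gives a list of known toxicities that also includes sleep paralysis, hallucinations around sleep and cataplexy-like symptoms, together with worsening depression and suicidal thinking.

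Mood and suicidality have a structured instrument. Section IX says: "Participants complete the PHQ-9 at study visits while on medication". An automatic alert and staff review before the visit ends go with it.

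**The concern.** A method that waits for the participant to volunteer an event is weakest for events she does not know have happened, and the protocol itself says that some serious effects of this drug are of that kind. The clinician query could close part of the gap, but its content is left open for everything except suicidal ideation. A general question about how she has been may bring out no more than she would have volunteered.

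Two things depend on the answer. At the Interim Treatment Visit (Visit 3) the dose step is conditional on limiting side effects, so it relies on those effects having been recognised and recorded. The review by the Medical Monitor and the monthly review by the Independent Safety Monitor both come after capture, and neither can act on an event that was never recorded.

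**Working it through.** The plan states no adverse-event count, detection rate or safety power, so there is no figure of its own to reproduce. The check is mainly a comparison of texts.

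**Which effects have a targeted route of capture?**

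| Effect | Named in | Said to be possibly unknown to the participant? | Targeted item on treatment |
|---|---|---|---|
| Worsening depression, suicidal thinking | Section V, Drugs to be used | No | PHQ-9 and CES-D at Visits 3 and 4; direct query on suicidal ideation |
| Daytime sleepiness | Sections V and VII | Yes (Section VII) | None found |
| Clouded thinking, odd or confused behaviour | Section VII | Yes | None found |
| Driving or other acts during sleep | Sections V and VII | Yes (Section VII) | None found |
| Sleep paralysis, hallucinations, cataplexy-like symptoms | Section V, Drugs to be used | No | None found |

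The nearest listed measure to daytime sleepiness is the Hyperarousal Scale. Section V describes it as a measure of trait arousal, and the Table of Procedures schedules it at Visits 2 and 4 only, so it is not available at Visit 3. No procedure asks for an observer's account.

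**When does the query apply?** Both descriptions limit it to visits on medication, which are Visits 3 and 4. The Table of Procedures marks adverse-event reporting at Visits 1 to 4, but no clinician query is specified before dosing. There is therefore no specified baseline for complaints, such as sleepiness, that women with insomnia may already have.

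**Illustration of what incomplete capture does in a trial of this size.** Inputs:

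- Women on suvorexant: up to 72 randomised 1:1 (Section V, Drugs to be used), so 72 / 2 = 36.
- True risk p: assumed, 2% and 1%. The documents give no rate for sleep behaviours, sleep paralysis, hallucinations or cataplexy-like symptoms.
- Share s of events that are recorded: assumed, 1, 0.5 and 0.25. The documents give none.

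Expected recorded events = 36 × p × s. Chance of recording at least one = 1 − (1 − p × s)^36.

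| p | s | Expected recorded | Chance of at least one |
|---|---|---|---|
| 2% | 1 | 0.72 | 1 − 0.98^36 = 0.52 |
| 2% | 0.5 | 0.36 | 1 − 0.99^36 = 0.30 |
| 2% | 0.25 | 0.18 | 1 − 0.995^36 = 0.17 |
| 1% | 1 | 0.36 | 1 − 0.99^36 = 0.30 |
| 1% | 0.5 | 0.18 | 1 − 0.995^36 = 0.17 |
| 1% | 0.25 | 0.09 | 1 − 0.9975^36 = 0.09 |

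The 7 in 100 for next-day drowsiness in Section VII is not used as a true risk. It is the rate that people reported in previous studies, so a further discount for non-reporting could count the same loss twice.

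**The case against.** The strongest reply is that spontaneous report is not the only route. Section V (Intervention design) provides a direct clinician query about other adverse events on medication, and Section IX repeats it in softer words. The two descriptions can be read as layers: staff note what is volunteered at every visit, and a clinician also asks while the woman is on treatment. That reading is reasonable, and a reader who inferred from the three spontaneous-report statements that nobody asks about adverse events would be wrong. What remains is that the documents do not say the methods are layered, do not say which feeds the adverse-event record, and do not say what is asked.

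A reader might also infer that all the named toxicities are affected. Depression and suicidality are not, for the reasons tabulated above. Sleep paralysis, hallucinations and cataplexy-like symptoms lack a targeted item, but nothing in the documents says that women are unaware of them.

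It can fairly be added that sample size is a limit whatever the method: even with full capture, a 2% event has only about an even chance of being seen once in 36 women. Both arms are also assessed by the same methods under blinding, so having two methods does not by itself bias the comparison between arms. Finally, yes/no questions put to the participant cannot reveal what she does not know. Only an account from someone else could, and only where someone else is present. All of this stands, and it limits how much the fix can achieve.

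**Conclusion.** The point holds as a gap in specification. The documents describe adverse-event capture in two ways without joining them, and the query has no stated content for the effects that Section VII says may go unnoticed or for sleep paralysis, hallucinations and cataplexy-like symptoms. These effects may be under-recorded, including at Visit 3.

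The documents do not support saying that they will be under-counted. No capture rate is given, so the size of any shortfall cannot be determined. The 52%, 30% and 17% rest on an assumed 2% risk and assumed capture shares; they show only that incomplete capture would matter in an arm of 36.

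Nor does the gap undermine a planned conclusion. Sections II and VI list no safety or tolerability hypothesis or endpoint, so what is at stake is what the safety data could support and what is on record during the trial. This is a cheap improvement to safety ascertainment and leaves the primary analysis untouched.

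**What to change.** 1. Reconcile the Treatment period and Intervention design paragraphs of Section V, the risk text of Section VII, and the suicidal-ideation and Adverse Event Reporting text of Section IX. State how spontaneous report and clinician query fit together and how each enters the adverse-event record.
2. Script the existing clinician query with short yes/no items naming daytime sleepiness, clouded thinking, odd or confused behaviour, acts during sleep, sleep paralysis, hallucinations and cataplexy-like symptoms. Add one item on what others in the household have observed, with a response for women who have no observer.
3. Ask it in identical words in both arms at Visit 2 (before dosing), Visit 3 and Visit 4, and by telephone if the final visit is remote.
4. Tabulate solicited events by arm, separately from spontaneously reported ones.

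The cost is about ten questions at visits that already exist and one extra table. Visit 2 is the only visit where a query is not already described. The downside is that more minor events will be elicited in both arms, which the separate tabulation is meant to handle. No dose or stopping rule is proposed.

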3. DSM-5 criteria for Insomnia Disorder.

4. Score on the Insomnia Severity Index (ISI) measure ≥ 15 , indicating at least a moderate level of insomnia symptoms
5. Subjective sleep disruption reported retrospectively over the past month and confirmed prospectively on a 7-day sleep diary shows:
 - a. < 9 hours average for subjectively reported total sleep time (TST).
 - b. 30+ minute average for subjectively reported wake after sleep onset (sWASO).
 - c. Sleep parameter in inclusion criteria 5a does not decrease by more than 50% on a 2nd week of sleep diary monitoring obtained after the screening visit.
 - d. Sleep parameter in inclusion criteria 5b does not both decrease by more than 50% and fall below 30 minutes on average on a 2nd week of sleep diary monitoring obtained after the screening visit.
6. Average of 2 or more hot flashes per 24 hours, at least some of which occur each night, reported retrospectively to have occurred over the past month and confirmed prospectively on one 7-day hot flash diary
7. Subjective report that at least some awakenings co-occur with night time hot flashes.

Exclusion criteria:

1. Sleep factors:
 - a. Diagnosis, or strong clinical suspicion, of other primary sleep disorders: obstructive sleep apnea, periodic limb movement disorder, narcolepsy, or RLS
 - b. Shift workers
 - c. Use of hypnotic medications more than twice per week in the past month
 - d. Willingness to not use other sedative-hypnotics during the study period
2. Psychiatric factors:
 - a. Current major depressive episode, by report and as indicated by the Patient Health Questionnaire (PHQ-9)
 - b. Current suicidal ideation
 - c. Lifetime history of bipolar disorder, psychosis, or other serious mental health problem
 - d. Current alcohol/substance use disorder
3. Medical factors:
 - a. Abnormal vital signs at screening visit
 - b. BMI ≥ 40 kg/m²
 - c. Renal or hepatic disease judged to interfere with drug metabolism and excretion
 - d. Pregnancy or breastfeeding
 - e. Malignancy within past 2 years
 - f. Major surgery within past 3 months
 - g. Neurological disorder or cardiovascular disease raising safety concerns about use of suvorexant and/or judged to interfere with ability to assess efficacy of the treatment
 - h. Medical instability considered to interfere with study procedures
 - i. Concomitant medications with drug interaction or co-administration concerns
 - j. Contraindications or allergic responses to suvorexant
4. Lifestyle and other factors:

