At the Randomization Visit, a one-week supply of suvorexant 10-mg pills or identical placebo will be given to each participant. Participants will be instructed to start taking 10-mg nightly for the first 7 days. At the Interim Treatment Visit conducted after one-week on treatment, the dose will be increased up to 20-mg nightly unless there are dose-limiting side effects. After the Interim Treatment Visit, women unable to tolerate a 20-mg dose will be given the option to reduce to a 10-mg dose. Consistent with FDA-approved directions, suvorexant will be started at 10-mg to first establish tolerability and then expected treatment efficacy will be optimized by increasing to the target 20-mg dose 7 days later. Women who are unable to tolerate the 10-mg dose will be dropped from the study. Any unused medication will be returned at the Final Treatment Visit, and unused pills will be counted as an indicator of adherence. Participants will not be informed of their treatment assignment at the Final Treatment Visit to maintain the blinding for study personnel. Participants who choose to stop participating in the study will be asked to complete remaining study questionnaires remotely. In this case, participants will return unused medication by mail.

V. STUDY PROCEDURES

Study Procedures and Outcome Measures

This study is a parallel-arm randomized trial involving 4 in-person study assessments conducted over approximately 6 weeks, during which participants will be randomized to receive double-blinded suvorexant 10–20 mg/day or placebo for the final 4 weeks of the study. See attached Table of Procedures for all study procedures. Details describing individual study procedures and surveys are provided below:

Screening period: There are 3 phases to our screening procedures: 1) an initial screening conducted via REDCap and over the phone, 2) prospective sleep and hot flash diary screening process completed over 14 days, and 3) final screening conducted at and after the in-person Screening Visit. We have found this phased screening approach to be highly efficient and readily approved by our Institutional Review Board. Consent to screen will be obtained orally on the phone for the initial screening procedures and diaries, and written informed consent will be obtained at the Screening Visit for the remaining screening procedures and all treatment-related procedures. Risks and benefits associated with use of suvorexant will be described.

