Sleep Assessment	Sleep Diary ^b					→
	Actigraphy Watch ^c		→			→
	ISI	X		X	X	X
	PSQI			X		X
	DBAS			X		X
	Sleep Locus of Control Scale			X		X
Hot Flash Assessment	Hot Flash Diary ^b					→
	Hot Flash Monitor ^a HFRDIS		→	X		X
Hyperarousal	Salivary Cortisol		→			→
	Hyperarousal Scale			X		X
	PSAS			X		X
Exploratory Measures	PHQ-9		X		X	X
	CES-D			X	X	X
	ASI-3			X	X	X
	GAD-7			X	X	X
	MENQOL			X		X
	PGI (Severity & Improvement)		X		X	X

Study procedures completed between study visits: a = for 24 hours; b = daily for 6 weeks; c = daily for 1 week DSM-V¹ = Diagnostic and Statistical Manual of Mental Disorders, 5th Edition, HCG = Human Chorionic Gonadotropin, FSH = Follicle Stimulating Hormone, ISI = Insomnia Severity Index, PSQI = Pittsburgh Sleep Quality Index, PSAS = Pre-Sleep Arousal Scale, DBAS = Dysfunctional Beliefs and Attitudes about Sleep Scale, HFRDIS = Hot Flash Related Daily Interference Scale, PHQ-8 = Patient Health Questionnaire Depression Scale, CES-D, Center for Epidemiological Studies Depression Scale, ASI-3 = Anxiety Sensitivity Index, GAD-7= General Anxiety Disorder Questionnaire MENQOL = Menopause-Specific Quality of Life Questionnaire, PGI-Patient= Clinical Global Impression Scale – Patient

Study assessments and procedures include the following:

1. Insomnia and sleep quality symptoms will be measured using:
 1. DSM 5 diagnostic interview for chronic insomnia. A clinical diagnosis of chronic insomnia will be made using the DSM-V diagnostic interview, allowing for associated hot flashes (see Inclusion Criteria).
 2. Sleep diary. Consistent with research consensus guidelines of insomnia,²⁵ a standard daily sleep diary will be completed to quantify perceived total sleep time, sleep latency, wake time after sleep onset, number of awakenings, sleep efficiency, and sleep quality.
 3. The Actiwatch actigraphic watch (Philips Respironics, Murrysville, Pennsylvania) will be worn on the non-dominant wrist to quantify sleep patterns based on acceleration and movement and the data output will be analyzed using standard actigraphic analysis algorithms.
 4. The Insomnia Severity Index (ISI), a 7-item self-rated questionnaire (range 0–28) used to assess the severity of insomnia symptoms over the past 2 weeks.²⁶
 5. The Pittsburgh Sleep Quality Index (PSQI), a 19-item self-rated measure of global sleep quality (range 0–21) occurring during the past one-month.²⁷

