Biolog skin conductance hot flash monitor: This is a widely used and validated ambulatory skin conductance monitor (UFI, Morro Bay, CA) that will be worn to quantify the number of objectively measured hot flash events by detecting changes in skin conductance on the sternum. This approach measures physiologic hot flashes independent of recall for the events, thereby eliminating potential recall bias for nighttime events.

Surgical Interventions

No surgical interventions will be used in this study.

VI. BIostatistical Analysis

Overview of analytic plan: The primary hypothesis for this trial is that suvorexant is superior to placebo in treating insomnia symptoms. The primary endpoint is the change in the ISI score from

baseline to 4-week follow-up. Exploratory analyses will examine the effect of suvorexant relative to placebo on secondary endpoints of sleep continuity parameters and diary-reported hot flashes, and exploratory endpoints including mood, anxiety, hot flashes (skin-conductance monitor), physiological stress (salivary cortisol), and quality of life.

Study endpoints:

Primary endpoint:

1. The primary endpoint is the change in the ISI score from baseline to 4-week follow-up.

Secondary endpoints:

1. Diary-reported WASO, SOL, TST, and sleep efficiency
2. Number of hot flashes reported on the diary separately during the day and night

Exploratory endpoints:

1. Actigraphy-measured WASO, SOL, TST, and sleep efficiency
2. Depressive symptoms
3. Anxiety symptoms
4. Quality of life
5. Number of hot flashes measured on the skin-conductance monitor
6. Physiological Stress (measured by salivary cortisol)

Primary analysis: The primary analysis will compare the within-person change in outcomes at Week 4 relative to baseline using general linear models, adjusting for baseline values and relevant covariates showing group differences at baseline. Diagnostic methods will be used for all models to assess their distributional assumptions, model adequacy, and to examine potential outlying or influential data points. An additional exploratory ISI responder analysis will be conducted using logistic regression to determine whether there is a group difference in the proportion of women that had a 8-point reduction in the ISI score from baseline.⁴¹

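### Does Section VI need to say which pre-treatment diary week is the baseline for the secondary endpoints?

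*Combined protocol and SAP*

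**What the plan says.** The primary-analysis paragraph of Section VI says the analysis will "compare the within-person change in outcomes at Week 4 relative to baseline using general linear models, adjusting for baseline values" and for covariates on which the groups differ at baseline. It does not define baseline.

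The secondary endpoints in the same section are "Diary-reported WASO, SOL, TST, and sleep efficiency" and "Number of hot flashes reported on the diary separately during the day and night".

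The footnote to the Table of Procedures gives the diary schedule as "b = daily for 6 weeks". The treatment-period text in Section V says "Participants will complete sleep and hot flash diaries for the 4 weeks they are on treatment". The screening text in Section V describes a "prospective sleep and hot flash diary screening process completed over 14 days".

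The eligibility rules in Section III treat the two weeks differently. The first must show average sWASO of at least 30 minutes. For the second, criterion 5d asks only that sWASO "does not both decrease by more than 50% and fall below 30 minutes on average on a 2nd week of sleep diary monitoring". Hot flashes are "confirmed prospectively on one 7-day hot flash diary".

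For the ISI, the Pre-Screening text in Section IV lists the full written form at Visits 3 and 4. The Table of Procedures has it before V1 and at V2, V3 and V4.

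**The concern.** A change score needs a starting value, and for every secondary endpoint the plan offers two candidate weeks and their mean. The weeks are not equivalent. The first carries the entry thresholds and is when users of sleep medication are asked to stop. The second follows the screening visit and is subject to a looser sWASO rule.

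The choice affects the estimates for wake time after sleep onset and hot flash frequency, which are hypotheses 1a and 1c in Section II. If it were made after unblinding, the reported result could be the most favourable of several, and a reader could not tell. The missing V2 entry in Section IV makes it look as if even the primary endpoint might lack a written baseline.

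**Working it through.** **Counts.** Six diary weeks less four on treatment leaves 6 − 4 = 2 before treatment. Four sleep measures plus two hot flash counts make 4 + 2 = 6 secondary endpoints.

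**What the text says about each week.**
- *First week.* Section IV describes these diaries as a way to spare women a screening visit for which they would not qualify. They are kept under oral consent to screen.
- *Second week.* Section V (Drugs to be used) separates a screening week from a run-in week. The run-in diary is kept after written consent, in the period when the actigraph and skin-conductance monitor are also worn, and is brought to V2. Section V (Treatment period) places pre-treatment symptom measures at V2. The end of treatment mirrors this, with the devices worn before V4.

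The run-in week is therefore the natural baseline, although this is inferred. On the outcome side, Section VI fixes Week 4, so an average over several treatment weeks is not an open option.

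**What baseline does in the model.** With outcome Y, baseline B and arm T, the model is Y − B = α + τT + βB. Rearranged, Y = α + τT + (1 + β)B. The treatment effect τ is the same as in a covariance analysis of the Week 4 value. B enters only as a covariate measured before randomization, so its choice alters precision and chance variation but does not bias τ. A shift or rescaling of B common to all women leaves τ unchanged. In simulation, multiplying week 2 by 0.8 (nightly CV 0.75, correlation 0.7) moved the median gap between the two estimates only from 4.27 to 4.31 minutes.

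**Individual women.** A woman with 128.7 minutes in week 1 and 30 in week 2 has fallen by 1 − 30/128.7 = 77%. She still passes 5d because she is not below 30. Her baseline could be 128.7, 30 or (128.7 + 30)/2 = 79.4 minutes.

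**Trial level, by simulation for diary WASO.**
- *From the protocol:* mean 128.7 and SD 67.9 minutes (Preliminary Data, n = 6); nightly CV below or near one; 30 per arm.
- *Assumed:* CV 0.5, 0.75 or 1.0; correlation of the log true means at baseline and on treatment 0.5, 0.7 or 0.9; lognormal person means; gamma weekly means; no drift between the two pre-treatment weeks.
- *True between-woman variance V:* V + CV²(128.7² + V)/7 = 67.9², giving SDs of 62.3, 55.1 and 44.3 minutes.
- *Runs:* 20,000 trials with no effect and 10,000 per effect size. Eligibility was week 1 ≥ 30 minutes together with rule 5d.

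| Quantity | Result |
|---|---|
| False positives, one fixed baseline | 4.6%–5.0% |
| False positives, best of week 1, week 2 and 14-day mean | 5.9%–8.5% |
| Gap between week-1 and week-2 estimates | median 2.5–5.6 min; 90th percentile 7.1–14.4 min |
| Verdict at p < 0.05 differs, 20% effect (0.20 × 128.7 ≈ 26 min) | 8%–19% of trials |
| Same, 30% effect (about 39 min) | 4%–11% |
| Same, 40% effect (about 51 min) | 0%–2% |
| Standard error, one week against the 14-day mean | 1%–6% larger |

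**ISI.** V2 is the only pre-treatment visit at which the table schedules the ISI. Section V refers to that table for all procedures. The phone repeat in Section IV applies only when a visit is delayed. V2 is therefore the baseline, and the list in Section IV omits it by a slip.

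**Primary power.** The inputs are a 4-point difference, SD 4.86, 30 per arm and two-sided alpha 0.05. Then 4/(4.86 × √(2/30)) = 3.19 and 3.19 − 1.96 = 1.23, a power of 89% (88% by the t-test). This exceeds the stated 80%. No input depends on a diary window.

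**The case for a change.** The best case for a change is that the run-in week is nowhere named as baseline. The rule in Section V names a visit, and both diary weeks end before it. It is also not universal, since the PHQ-9 is given at V1 and not at V2. Criterion 5d lets the weeks diverge widely for a given woman. The conditions for unblinding under Independent Safety Monitor in Section IX are completed safety reviews, identified protocol violators and complete data; settled analysis definitions are not among them. Covariates are chosen by baseline differences, so the window could also affect the covariate set. One paragraph would close the gap at no cost in data.

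It stands that the definition is unwritten and that, with modest effects, two defensible windows can fall on opposite sides of 0.05. That last point is ordinary sampling variation between two valid analyses near a threshold. The inflated error rate requires someone to compare results and report the best. Section IX keeps study personnel blinded until the data are complete, which gives a natural moment to settle the window, although it does not compel it. The PHQ-9 is not ambiguous, because it has a single scheduled pre-treatment administration.

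The plan also claims no confirmatory error rate here. Section II heads these hypotheses as exploratory, and Section VI describes the secondary analyses in the same way. Six unadjusted tests, if independent, already carry 1 − 0.95⁶ = 26% chance of at least one false positive. A rise of about 1 to 3.5 points per endpoint is small beside that.

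**Conclusion.** No change is needed. The diary baseline is a missing detail that an analyst would sensibly fill with the run-in week, and the Section IV list is a clerical slip that the Table of Procedures resolves. Any single pre-treatment window used for both arms is valid, with 4.6%–5.0% false positives, and using one week instead of two costs 1%–6% in standard error. The worst case is 5.9%–8.5% per endpoint. It depends on selection after unblinding, which the plan does not call for, and it concerns exploratory endpoints.

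The simulated figures are for diary WASO only. They rest on a mean and SD from six women and on assumed nightly CVs and correlations. No figure is offered for SOL, TST, sleep efficiency or hot flashes. The argument that any one fixed window is unbiased does not depend on those inputs. The primary ISI comparison is unaffected.
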